a. Weekly global symptom assessment will be measured through adequate relief of dyspepsia symptoms during the prior week (48,49). This self-report measure is considered clinically relevant and has been tested for responsiveness in functional dyspepsia (50,51).

b. Disease-specific validated Nepean Dyspepsia Index (NDI) (**Appendix 6**) will be used to assess functional dyspepsia quality of life (52) at baseline and post-treatment. NDI scores are summarized as overall quality of life and 5 subscales: interference, knowledge/control, eating/drinking, sleep disturbance, work/study (range: 0 to 100) (52). NDI also evaluates mean symptom scores for abdominal pain and postprandial distress.

c. Validated daily symptom diaries assessing upper abdominal pain, nausea, bloating, fullness, and early satiety on a scale of 0 to 3 (0 nil; 1 mild; 2 moderate; 3 severe) using a validated instrument (53) and simply tabulating the information.

d. Leuven Postprandial Distress Scale (LPDS), the most validated symptom scale available with psychometric evidence supporting the LPDS's individual items, as well as evidence of responsiveness to treatment (54-56), comprises eight symptoms (early satiation, postprandial fullness, upper abdominal bloating, epigastric pain, epigastric burning, nausea, belching and heartburn) with verbal descriptors rated for severity (0-4). The symptoms early satiation, postprandial fullness, and upper abdominal bloating constitute the most valid symptom group for postprandial distress in FD with an established minimal clinically important difference.

e. Functional Dyspepsia Symptom Diary (FDSD), a content-valid measure (57), with psychometric evidence supporting the FDSD's individual items (stomach pain, stomach burning, nausea, bloating, stomach fullness,

early satiety, burping/belching rating, burping/belching bothersome) measured on 11-point (0-10) scale and total score (stomach pain, stomach burning, bloating, stomach fullness, early satiety: maximum score of 50).

Pharmacogenomics: Collection and storage of venous blood for DNA studies: All participants in the trials in aim 1 will have 10mL venous blood sample for DNA extraction and storage. Genotyping of FAAH (rs324420), and CNR1 (rs806378) will be performed using Taqman™ SNP Genotyping assays (Applied Biosystems Inc., Foster City, CA, USA) in accordance with the manufacturer's instructions.

Rationale for the selection of candidate cannabinoid genetic polymorphisms

CNR1 (the gene for CB1 receptor) has 2 synonymous single nucleotide polymorphisms (SNPs), rs35057475 and rs1049353; neither results in a change in amino acid sequence. There is an (AAT) n repeat at the 3' end of CNR1, 18,000 bases downstream from the start site of exon 4 of CNR1. The number of repeats is highly variable (from 2 to 6 repeats) and, although associations with psychiatric disease, i.v. drug use, and response to antipsychotics have been described (58-62), the functional significance of this genetic variation is unclear. The T allele of **CNR1 polymorphism rs806378** is associated with altered nuclear protein binding in an electrophoretic mobility shift assay, suggesting that rs806378 is a **functional** polymorphism (63). We previously demonstrated **association of this genotype** with gastric and colonic functions (see Background).

FAAH 385C to A allelic variant (rs324420) leads to a Pro129Thr amino acid sequence change, which decreases expression of the FAAH protein due to reduced protein stability (64). The prevalence of the A allele is 16%–25% in studies of Caucasians in the NCBI database. Our laboratory has previously confirmed the A allele frequency to be 25% in our sample population of healthy controls and IBS patients in southeastern Minnesota (18). Reduction in FAAH protein level and activity compromises inactivation of the endocannabinoid anandamide, which leads to higher synaptic concentrations of anandamide and resulted in a greater effect of the exogenously administered cannabinoid agent, dronabinol, via activation of CB1 and CB2 receptors.

In addition, we shall screen patients' **CYP3A4** and **CYP2C19** genes, which impact the main CYP450 enzymes responsible for cannabidiol metabolism (65). Ultra-rapid metabolizers for CYP2C19 [estimated 17% and 18% based on literature review (36)] will be excluded since this could impact assessment of effects of cannabidiol.

General Approach for Statistical Analyses

- Abdominal pain score on NDI in functional dyspepsia (aim 1b)
- Proportion of responders based on adequate relief in functional dyspepsia (aim 1b)
- Average daily aggregate symptom score for upper abdominal pain, nausea, bloating, fullness, and early satiety (each on a scale of 0 to 3) in functional dyspepsia (aim 1b)

LPDS score and FDSD scores will be exploratory endpoints since they have only recently been validated.

Sample Size Assessment

This is based on results of the primary endpoints in our Mayo Clinic lab. Expected (80% power, $\alpha=0.05$, assuming parallel-group study and unpaired analysis with $n=22$ in aim 1a and **n=24 aim 1b**) demonstrable differences compared to placebo show that the study is powered to detect clinically relevant effects of cannabidiol based on the variation (SD) observed from our Mayo prior studies (42-44,46,47).

TABLE 3. Sample Size Assessment: Response	Mean	SD	Effect size detectable (absolute [% of mean], $n=24$ per group)
Fasting gastric volume, mL	273	57	47mL (17%)
Postprandial gastric volume, mL	848	111	91.7mL (10.8%)
Gastric emptying of solids $T_{1/2}$, min	122	29.8	24.62 (20.2%)
Volume to fullness, mL	755	330	273mL (36.2%)
Maximum tolerated volume, mL	1283	400	330.5mL (25.8%)
Δ from baseline in average (of 3 subscales in) GCSI-DD	-1.4	0.5	0.413 (29.5%)
Average Aggregate Symptoms Score for dyspepsia	1.42	0.64	0.50 (35.2%)
NDI overall quality of life score	63.6	22.5	18.6 (29.2%)
NDI abdominal pain score	29.4	10.4	8.6 (29.3%)
NDI postprandial distress score	12.8	7.5	6.2 (48.4%)

Therefore, the study has sufficient power to detect clinically relevant effects on quantitative traits. The study will provide important information on the mean response in clinically important endpoints in the two trials and, therefore, provide important preliminary information, such as coefficient of variation of the response in the current hypothesis-generating trials in order to plan future hypothesis-testing trials.

Interim Analysis: As part of an on-going method to compare the effects of each medication tested and placebo, an interim analysis will be conducted when 50% of the first specific aim has been reached.

Rationale for Interim Analysis:

- To assess power of the study based on the actual coefficient of variation as measured in the actual study with >50% completed; this is because the coefficient of variation could be different from the COV used in the a priori power calculation used in development of the protocol.
- As part of the analysis, the statisticians will also provide a comparison of the results on the primary and secondary endpoints; this assessment will be communicated to the investigators as average data (e.g. median and IQR) for the treatment GROUPS rather than individual patient data. These group data could be used for preparation of preliminary reports in the form of abstract for national meetings specifically, Digestive Disease Week to be held in May 2021 for which the deadline for abstract submission is December 1, 2020.
- As a result of the power analysis, it is possible that the sample size may be either reduced or increased or the study could be stopped because of “futility” if there is no evidence of a trend to suggest efficacy of treatment.

Outcome of Interim Analysis:

In accordance with the approval from IRB to conduct an interim analysis after 50% of planned participants with gastroparesis had completed the study activities according to protocol, the data of 24 patients (that is 50% of the number originally proposed for the study) were analyzed by the study statistician, [name] MS.

The **objective of the interim analysis** is to determine what is the SAMPLE SIZE (currently planned at 24 per treatment arm, that is cannabidiol vs placebo, 1:1 ratio) required, based on the current data (group difference and coefficient of variation) to demonstrate EFFICACY based on the STATED PRIMARY endpoints in the NIH grant application:

Primary endpoints: Physiological traits and patient reported outcomes for cannabidiol vs. placebo groups:
 (a). Gastric emptying T1/2 solids

- (b). Fasting and accommodation gastric volumes
- (c). Satiation by the maximum (max) tolerated volume
- (d). Average daily (total) GCSI-DD score

Secondary endpoints:

1. Satiation assessed by the volume to fullness
2. Aggregate symptom score 30 min. after max. tolerated volume
3. GCSI-DD subscores of: nausea, vomiting, postprandial fullness, satiety, bloating, pain

Based on Δ values, a positive number indicates an improvement in the parameter on treatment relative to baseline. A priori, conditional power of <0.20 was identified as indicative of futility to continue the trial. Given that several parameters of interest were associated with conditional power >0.20 , and the sample size required to identify clinically important differences with $n<24$ per treatment group (which was originally planned in study protocol), the conclusions reached following the interim analysis were:

1. To continue the clinical trial with the same treatments (cannabidiol and placebo)
2. Reduce total sample size from 48 to 44
3. Retain strategies of concealed allocation, study blind of all investigators on the study

With larger sample size in the two treatment groups, it is conceivable that the SD and coefficient of variation will be smaller in the final study database, thereby providing potential to appraise other endpoints shown in the table, such as upper abdominal pain, maximum tolerated kcal, and GE $T_{1/2}$.

Subsequent Interim Analysis: As part of an on-going method to compare the effects of each medication tested and placebo, a subsequent interim analysis will be conducted when $>85\%$ of the gastroparesis group participants have completed study procedures.

Rationale for Subsequent Interim Analysis:

The objective of the interim analysis is not to change the current goal of evaluating 44 patients randomized to either cannabidiol or placebo as is currently detailed in the statistical analysis plan and was confirmed following an interim analysis performed for the purposes of evaluating statistical power and appropriate sample size.

This subsequent interim analysis is intended to provide an evaluation of data collected from more than 85% of the gastroparesis group participants. In this analysis, statisticians will provide a comparison of the results on the primary and secondary endpoints; this assessment will be communicated to the investigators as average data (e.g. median and IQR) for the treatment GROUPS rather than individual patient data in order for the investigators to remain blinded to the individual participant data and to the treatment group to which each individual had been assigned by randomization. These group data would be used for preparation of preliminary reports in the form of abstract for national meetings, specifically Digestive Disease Week to be held in May 2023, for which the deadline for abstract submission is December 1, 2022.

Approval of this request for the subsequent interim analysis is necessary for the research pharmacy to send the randomization code exclusively to the statistician.

APPROACH

AIM 1a: Effects of treatment with cannabidiol on gastric functions, satiation and symptoms in patients with gastroparesis

Hypothesis 1a: Cannabidiol enhances gastric accommodation and reduces post-nutrient challenge symptoms without altering gastric emptying in patients with gastroparesis.

Specific Aim 1a: To compare effects of cannabidiol vs. saline on satiation, fasting gastric volume, gastric accommodation and emptying, and GCSI-DD in patients with gastroparesis

Rationale: Cannabidiol has multiple effects on GPCRs, 5-HT_{1a} receptors and neuroprotection to potentially impact gastric functions and pain in patients with gastroparesis. Pain is a significant unmet need in patients with gastroparesis. In the NIH Gastroparesis Consortium Patient Cohort, the predominant symptoms in 393 patients were pain/discomfort in 21% and nausea/vomiting in 44%. Pain was rated moderate or severe in 66% of those with pain. Idiopathic gastroparesis (256 patients) was correlated with opioid and antiemetic use, depression, anxiety, and poor QOL. Pain presentation was also not associated with the results of gastric emptying test, or with diabetic neuropathy or control of diabetes (69).

Experimental design: We will perform a randomized, double-blinded, placebo-controlled study of cannabidiol, 20mg/kg/day (achieved after dose escalation), and placebo, each in two divided doses with n=22 per treatment arm. All participants will have gastroparesis symptoms, prior documentation of delayed gastric emptying (GE) at Mayo Clinic, and will undergo *baseline measurements of GE to be used as a covariate* in assessing the response to treatment with cannabidiol.

Randomization will be stratified on gender and BMI.

Experimental procedures and measurements: All participants will undergo measurements of GE of solids, gastric volume (fasting and postprandial), Ensure® nutrient drink satiation test (which also serves as a dyspeptogenic meal) and symptom assessment.

[figure not shown]
Details of each are provided in the Common Methods section.

Statistical analysis: ANCOVA will be used to compare the 2 treatment groups, including baseline GE $T_{1/2}$ as covariate.

Primary endpoints: Physiological traits and patient reported outcomes for cannabidiol vs. placebo groups:

- Gastric emptying $T_{1/2}$ solids
- Fasting and accommodation gastric volumes
- Satiation by the maximum (max) tolerated volume
- Average GCSI-DD score

Figure 9. Experimental protocol to compare the effects of cannabidiol and placebo in gastroparesis

Secondary endpoints:

- Satiation assessed by the volume to fullness
- Aggregate symptom score 30 min. after max. tolerated volume
- GCSI-DD subscales: nausea/vomiting, postprandial fullness/satiety, bloating

Statistical power: Addressed in the Common Methods/Statistics section

Anticipated results compared to placebo:

- Cannabidiol will increase fasting and accommodation gastric volumes, and calorie intake at satiation test without significantly retarding gastric emptying.
- Cannabidiol will reduce average weekly symptoms score based on GCSI-DD.
- We anticipate <5% dropouts due to medication intolerance or adverse events in this single-center study, consistent with experience from multicenter studies conducted in patients with syndromic seizures.

Potential pitfalls, precautions taken, and alternative strategies:

a. **Feasibility:** Given our 100-person database of patients with gastroparesis residing within 150 miles of Rochester, MN and with prior documentation of upper gastrointestinal symptoms consistent with gastroparesis, as well as documented delay in gastric emptying, we are confident that we can recruit the required number of participants for the studies that involve only noninvasive tests.

b. **Consideration of sex as a biological variable:** In our past cohort of 100 patients, 69% were female.

Therefore we anticipate recruitment of 44 patients will include sufficient numbers of male and female patients.

c. **Scientific premise for inclusion of both genders:** Although gastroparesis and functional dyspepsia are more prevalent in females, there is no a priori evidence that the effect of cannabidiol differs between genders and the pathophysiological mechanisms do not appear to be different between genders. Therefore, our study will assess treatment efficacy in **both genders**; we shall recruit numbers of men and women in ratio of 1:1.5.

d. **Drop-outs:** The hypothesis-testing study will utilize intention-to-treat principles. The analysis population will include all randomized subjects. We plan to include in the informed consent forms clear information to differentiate treatment discontinuation from study withdrawal, as well as a statement educating patients about the continued scientific importance of their data, even if they discontinue study treatment early. Therefore, patients will be followed after treatment discontinuation in order to preserve the ability to analyze endpoints for all participants who underwent randomization and, thus, to make possible intention-to-treat inferences (70).

e. **Missing data:** We shall explore three methods for data imputation:

(i) Imputation of any missing data for the primary endpoint (e.g. gastric emptying $T_{1/2}$) will use the overall mean $T_{1/2}$ for all subjects randomized, adjusting the error degrees of freedom (df) in the ANCOVA model by subtracting one df for each value imputed to provide a more accurate estimate of residual error variance.

(ii) Using a mixed-model repeated measures method, we shall assume that continuous repeated measures have a normal distribution with a specified form of mean and covariance matrix. With multiple imputations, multiple sets of plausible values for missing data will be created from their model-based predictive distribution, and estimates and standard errors will be obtained using multiple-imputation combining rules (50).

(iii) We shall use the last rank carried forward (LCRF) approach as described in O'Brien et al. (71).

In order to develop pre-specified monitoring and analysis plans, we shall establish a DATA SAFETY MONITORING PLAN which will involve review by experts independent of the study, using a team comprised of researchers with track records in biostatistics and clinical trials and expertise in the quantitative traits. We have established definite stopping rules for the trial.

Significance: This study will evaluate efficacy, safety, and mechanisms of action of cannabidiol in the largest single-center study to date, and it will provide information on the coefficient of variation in patient reported outcomes to plan future hypothesis-testing, multicenter studies of the effects of cannabidiol in gastroparesis.

AIM 1b: Acute effects of cannabidiol on gastrointestinal functions and symptoms in patients with functional dyspepsia and non-delayed gastric emptying

Hypothesis 1b: Cannabidiol enhances gastric accommodation and reduces post-challenge symptoms without altering gastric emptying in patients with functional dyspepsia with non-delayed baseline gastric emptying.

Specific Aim 1b: To compare the effects of cannabidiol vs. placebo on satiation, fasting gastric volume, gastric accommodation and emptying, and symptoms in patients with functional dyspepsia with normal baseline gastric emptying,

Rationale: A prominent pathophysiologic feature of functional dyspepsia is defective gastric accommodation, with inadequate relaxation of the fundus of the stomach in response to eating, which is responsible for the post-cibal pain. This was observed in 47% of 151 patients with functional dyspepsia in a Mayo Clinic study performed in the clinical practice of the PI (72). There are presently no generally effective medications to restore normal gastric accommodation, and there is only limited support, based on single-center studies, for

b. **Consideration of sex as a biological variable:** In the ~1270 person database, 60% were female (37). We anticipate a female to male ratio of 1.5:1 to ensure we can assess sex as a biological variable.

c. Scientific premise for inclusion of both genders includes: Although functional dyspepsia is more prevalent in females, there is no a priori evidence that the effect of cannabidiol differs between genders, and the pathophysiological mechanisms do not appear to be different between genders. Therefore, our study will assess treatment efficacy in **both genders, and we shall recruit ~ equal numbers of men and women.**

d. Drop-outs and missing data will be managed as for specific aim 1a.

Significance: This study will evaluate efficacy, safety, and mechanisms of action of cannabidiol in the largest single-center study in functional dyspepsia to date, and it will provide information on the coefficient of variation in patient reported outcomes to plan future hypothesis-testing, multicenter studies of the effects of cannabidiol in patients with functional dyspepsia.

Aim 2: Treatment by genotype interaction of cannabidiol and *FAAH* and *CNR1* genes and gastric functions in patients with functional dyspepsia or gastroparesis

Hypothesis 2: *FAAH* rs324420 and *CNR1* rs806378 genotype significantly affect the response of gastric accommodation, gastric emptying and satiation to treatment with cannabidiol in patients with gastroparesis or functional dyspepsia with normal baseline gastric emptying.

Specific Aim 2: To assess pharmacogenetics effects of variants in *FAAH* and *CNR1* genes on the pharmacodynamics effects of cannabidiol vs. placebo on gastric accommodation, gastric emptying and satiation in the same patients with gastroparesis or functional dyspepsia.

Rationale: In prior studies, *FAAH* rs324420 and *CNR1* rs806378 gene variants were associated with gene by treatment interactions on diverse gastrointestinal motor functions in response to the non-selective cannabinoid agonist DRO (see background). Genotype distributions (18,19) in participants in prior Mayo Clinic studies are shown in Figures 11 and 12. We have previously demonstrated

(18,19) the MAFs of the *FAAH* and *CNR1* variants in our catchment population are consistent with NCBI and other literature reports with *FAAH* MAF of 0.25 and *CNR1* MAF of 0.29.

Experimental design: From specific aim 1, there will be 46 patients (22 with gastroparesis and 24 with functional dyspepsia) treated with cannabidiol; we shall compare in these patients the association of gene variants on the effects of cannabidiol on gastric emptying using a dominant genetic model. The model will include cannabidiol, gene variants, plus the

[figure not shown]

Figure 11: *FAAH* rs324420 genotype distribution in FGID and healthy controls studied at Mayo Clinic and reported distribution in NCBI and in a study mostly in Caucasians.

[figure not shown]

Figure 12: *CNR1* rs806378 genotype distribution in FGID and healthy controls at Mayo Clinic (mostly Caucasians)

include gender, treatment (yes/no) interaction gene x treatment.

Experimental procedures and measurements: All participants will have undergone gastric emptying of solids, gastric volume (fasting and postprandial) and satiation test in specific aim 1. Genotyping for *FAAH* rs324420 and *CNR1* rs806378 and *CYP 3A4* and *2C19* will be performed. See common methods section.

Endpoints: (a) Gastric emptying $T_{1/2}$ solids; (b) Accommodation gastric volume; (c) Satiation by the MTV

Statistical considerations and analysis:

Applying the dominant genetic model, we anticipate there will be a 60:40 split of *FAAH* rs 324420 CC vs. CA/AA, and a 50:50 split for *CNR1*rs806378 CC vs. CT/TT.

Given there will be 46 participants receiving cannabidiol and assuming an approximate 50:50 split of the participants based on both genotypes (that is, 23 patients CC vs. 23 CA/AA *FAAH* rs 324420 or 23 CC vs. 23 CT/TT for *CNR1* rs806378), we anticipate the following effect sizes attributable to the gene variants (Table 4):

Table 4. Response	Mean	SD	Effect size detectable ([% of mean], n=24/ genotype group)
Fasting gastric volume, mL	273	57	47mL (17%)
Postprandial gastric volume, mL	848	111	91.7mL (10.8%)
Gastric emptying solids $T_{1/2}$, min	122	29.8	24.62 (20.2%)
Volume to fullness, mL	755	330	273mL (36.2%)
Maximum tolerated volume, mL	1283	400	330.5mL (25.8%)

ANCOVA will compare the genotypes for each gene variant, including baseline GE $T_{1/2}$ as covariate.

Anticipated results: Effect of cannabidiol will be significantly associated with *FAAH* and *CNR1* genotypes consistent with the hypothesis that the gene variants impact the function of the receptor target or the inactivation of endocannabinoids that modulate gastric motor functions, or calorie intake at satiation test.

Potential pitfalls, precautions taken, and alternative strategies:

Feasibility: The study participants will be enrolled in specific aim 1; the power calculation based on our patient community gene minor allele frequency shows that the study has sufficient power to detect clinically relevant gene * treatment interactions.

Genetic variation in metabolism (inactivation) of cannabidiol: Ultra-rapid metabolizers for *CYP2C19* [estimated 17% and 18% based on literature review (36)] will be excluded since this could impact assessment of effects of cannabidiol.

Consideration of sex as a biological variable: In the ~1270 person database, 60% were female (37). We anticipate a female to male ratio of 1.5:1 to ensure we can assess sex as a biological variable.

Scientific premise for inclusion of both genders includes: Although functional dyspepsia is more prevalent in females, there is no a priori evidence that the effect of cannabidiol differs between genders, and the pathophysiological mechanisms do not appear to be different between genders. Therefore, our study will assess treatment efficacy in **both genders, and we shall recruit men and women in the ratio 1:1.5**.

Drop-outs and missing data will be managed as for specific aim 1.

Significance: This study will evaluate impact of common functional genetic variants in CB1 receptor and cannabinoid inactivation on the pharmacodynamics responses to cannabidiol, potentially important in individualizing therapy with cannabidiol in the treatment of gastroparesis and functional dyspepsia that may impact plan and design of future hypothesis-testing, multicenter studies of the effects of cannabidiol in patients.

Overall Significance of Application: The proposed studies provide the ability to validate a recently approved pharmaceutical grade cannabidiol for the treatment and addressing the unmet need of millions of American citizens with gastroparesis or functional dyspepsia, including personalization of treatment based on genotype by treatment interactions. This research team is uniquely poised to deliver on this vision.

Time Table: **Years 1-4:** specific aims 1, 2; **Year 5:** data analysis and publications

LITERATURE CITED

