Common adverse events (>10% frequency) in the cannabidiol trials for childhood seizure disorders were somnolence, vomiting, fatigue, pyrexia, upper respiratory tract infection, decreased appetite, convulsion, lethargy, somnolence, and diarrhea. Elevated aminotransferase levels have been observed. In the trials to date, cannabidiol lacked the psycho-activity of the archetypal cannabinoid, Δ^9 THC, consistent with lack of appreciable affinity or activity at the cannabinoid receptors. Cannabidiol did not provoke suicidality. As a precaution, we shall use the approved assessment instrument, the Columbia Suicide Severity Rating Scale (Appendix 3) and the study team will assess the patients by phone at weeks 1 and 2, and in person at week 4. If suicidal thoughts and behavior emerge during treatment, the treatment will be discontinued.

Randomization: A randomization schedule, computer-generated by the study statistician's office, will be submitted to the Mayo Clinic CCaTS Research Pharmacy. Allocations will be concealed. Medications will be stored in a monitored, climate-controlled environment according to manufacturer's directions. Monitoring records will be available for review to ensure quality control.

[figure not shown]

Figure 7. SPECT measures gastric accommodation

one glass of skim milk (320kcal, 30% fat). Performance characteristics and normal values (214 female and 105 male volunteers) are published (43). A variable region of interest program will be used to quantitate counts in the stomach. Data will be summarized as GE $T_{1/2}$ and GE % emptied at 2 and 4 hours. Note that in healthy controls, gender, but not age or BMI, was associated with GE of solids (GE $T_{1/2}$, proportion emptied at 1 hour and 2 hours, all $p<0.001$) (43).

Table 2. Mean \pm SD for gastric emptying (healthy adults) using the same method (43)

	All controls, n=319	Male controls, n=104	Female controls, n=215
Age , y	36.2 \pm 13.1	34.6 \pm 13.3	37.2 \pm 12.8
BMI, kg/m ²	26.9 \pm 5.1	27.8 \pm 4.5	26.5 \pm 5.3
Solid GE $T_{1/2}$	121.7 \pm 29.8	109.9 \pm 28.6	127.7 \pm 28.7

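### Aim 2 compares genotypes in a pool of gastroparesis and functional dyspepsia patients with no stated disease term; baseline gastric emptying only partly replaces one for accommodation and satiation

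*Combined protocol and SAP*

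**What the plan says.** Aim 2, Experimental design, states that "there will be 46 patients (22 with gastroparesis and 24 with functional dyspepsia) treated with cannabidiol" and that gene variants will be related to response in these patients under a dominant model. The description of the model is interrupted by Figures 11 and 12. What is legible names cannabidiol and the gene variants, and resumes with "include gender, treatment (yes/no) interaction gene x treatment". Under Statistical considerations and analysis an unbroken sentence says "ANCOVA will compare the genotypes for each gene variant, including baseline GE" T1/2 as the covariate. The General Approach for Statistical Analyses adds gender, BMI and smoking as possible covariates, but not disease or trial.

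The endpoints are GE T1/2, accommodation volume and MTV. Sizing proceeds by "assuming an approximate 50:50 split of the participants based on both genotypes", that is 23 v 23, although the same section says "we anticipate there will be a 60:40 split of *FAAH* rs 324420 CC vs. CA/AA". The header of Table 4 uses a third figure, "n=24/ genotype group". Its five rows repeat the corresponding rows of Table 3, with one mean and one SD each.

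Under Participants Eligibility Criteria, gastroparesis requires slow emptying at 2 h and/or retention above 23.8% (females) or 23% (males) at 4 h. Functional dyspepsia requires less than 25% retained at 4 h. The interim table on sample size re-estimation places the nutrient drink results among the measurements that have no baseline.

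**The concern.** The two diseases are defined by gastric emptying, and emptying is an endpoint. Their satiation and accommodation levels may differ too. A pooled genotype comparison without a disease term puts any disease gap that the covariates do not absorb into the residual error. Genotype is not randomised, so if carriers and non-carriers differ in their share of gastroparesis patients, part of the gap is also read as a genotype effect. Aim 2 is meant to inform individualised therapy, and its feasibility text claims adequate power. Both depend on an error SD that fits the pooled sample.

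**Working it through.** **Reproducing Table 4.** Inputs: two-sample t-test, 80% power, alpha 0.05 (two-sided assumed), 24 per group. The detectable difference is 0.826 SD. For GE T1/2 (SD 29.8) this gives 24.62 min, as printed; for MTV (SD 400) it gives 330.45 mL, printed as 330.5. At the plan's own 23 v 23 the figures are 25.17 min and 337.9 mL. At 28 v 18 (46 x 0.6 = 27.6; 46 x 0.4 = 18.4) they are 25.79 min and 346.2 mL. Power for the printed differences is 78% and 76% respectively.

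**Whose SD.** The GE row (122, 29.8) is the value for 319 healthy volunteers (121.7 ± 29.8) in the gastric emptying tables. Interim gastroparesis baseline medians are 208.2 (n=10) and 198.4 (n=13) min, with values capped at 240. Weighted: (10 x 208.2 + 13 x 198.4)/23 = 203 min.

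**GE T1/2.** Assumptions: dyspepsia mean 122 and SD 29.8; gastroparesis mean 203 (gap 81); gastroparesis SD 29.8 to 48.9 (the upper value is the interim SD of change on cannabidiol, used as a proxy); baseline-to-post correlation 0.3, 0.5 or 0.7. Detectable difference in minutes at 23 v 23, by simulation:

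| Gastroparesis SD | Correlation | Baseline GE only | Baseline GE + disease | Reduction |
|---|---|---|---|---|
| 29.8 | 0.3 | 27.9 | 24.0 | 14% |
| 29.8 | 0.5 | 24.0 | 21.8 | 9% |
| 29.8 | 0.7 | 19.0 | 18.0 | 5% |
| 48.9 | 0.3 | 36.4 | 32.3 | 11% |
| 48.9 | 0.5 | 31.7 | 29.3 | 8% |
| 48.9 | 0.7 | 25.3 | 24.2 | 4% |

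**MTV.** First, how much of disease membership does baseline GE explain?
- Between-disease variance of GE: (22/46)(24/46) x 81² = 0.2495 x 6561 = 1637.
- Within-disease variance: 29.8² = 888, or (22/46) x 48.9² + (24/46) x 29.8² = 1607.
- Share explained: 1637/2525 = 0.65, or 1637/3244 = 0.50.

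If GE and MTV are unrelated within disease, 35-50% of the between-disease MTV variance stays in the error. Residual SD = sqrt(400² + (0.35 to 0.50) x 0.2495 x gap²). Power for 330.5 mL at 23 v 23:

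| Assumed gap, mL | Residual SD | Power |
|---|---|---|
| 0 | 400 | 78% |
| 300 | 410-414 | 75-76% |
| 640 | 443-459 | 67-70% |

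A gap of 643 gives 66-70%. The upper gap is 1283 - 639.5, the planning mean minus the interim placebo gastroparesis intake at 1 kcal/mL. It is not a gastroparesis-versus-dyspepsia difference.

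The interim gastroparesis SDs are 286.7 and 343.7. With 343.7 in both diseases and baseline GE in the model, power is 83-85% at a gap of 427 (1283 - 856.3, the cannabidiol arm) and 76-80% at 640. That is close to or above Table 4's 78%.

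**Accommodation volume.** No by-disease means or SDs are given, so no figure can be computed.

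**Disease mix by genotype.** With 22 gastroparesis patients among 46 and no true association with genotype, the hypergeometric probability that the gastroparesis share differs by at least 10 percentage points is 38% for a 23/23 split and 55% for 28/18. A 10-point imbalance with a 640 mL gap shifts the cannabidiol-only contrast by 0.10 x 640 = 64 mL without adjustment. With baseline GE in the model, and again no within-disease link between GE and MTV, about 35-50% of that remains: 22-32 mL.

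**The case against.** There are four fair points in favour of the plan.

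- **Baseline GE T1/2 is in the model.** A reader might compare the unadjusted pooled GE SD of about 50-57 with 29.8 and infer that Aim 2 loses most of its power for emptying. The documents do not support that: the planned covariate removes most of the gap, leaving the 4-14% shown above.
- **The MTV gap is not documented.** A reader might take 640 mL as the disease difference and infer a fall in power to about 57%. That needs the largest gap, an SD of 400 and no baseline covariate all at once. The planning mean is not a dyspepsia value, and dyspepsia entry itself requires bothersome fullness or early satiation.
- **Gene x treatment is largely protected from bias.** Treatment is randomised within each trial, so a disease gap associated with genotype is the same in both arms in expectation and cancels from the interaction. A biased interaction also requires treatment response to differ by disease, which nothing in the documents shows.
- **The text is damaged.** A disease term could have stood in the sentence broken by the figures. The eligibility criteria also overlap slightly, because gastroparesis can qualify at 2 h alone or just under 25% retained at 4 h.

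All four limit the size of the problem. None removes it: the intact ANCOVA sentence has no disease term, the cannabidiol-only genotype contrast is not protected by randomisation, and the interaction still loses precision. That the trials are described as hypothesis-generating lowers the stakes, but does not justify combining two trials without a trial term.

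**Conclusion.** The point holds at moderate size. No disease or trial term is stated in the readable Aim 2 text, although two separately randomised populations, selected largely on gastric emptying, are pooled. For GE T1/2 the consequence is small. It matters more for MTV and accommodation volume, where baseline GE is an indirect proxy and, for the nutrient drink test at least, there is no own baseline.

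For MTV, power for 330.5 mL is about 78% with no gap and 66-70% at the upper end of the assumed 0-640 mL range, given a within-disease SD of 400. If the SD is nearer the interim 287-344 there may be no shortfall against Table 4, though a disease term would still recover precision whenever a gap exists.

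A real difference in genotype frequency between the diseases would bias the cannabidiol-only contrast. A chance imbalance distorts the estimate in the sample obtained, which is the same phenomenon as the added error variance and not a further loss. Separately, Table 4 rests on single-population SDs (healthy volunteers for GE T1/2) and on 24 per group, which the plan's 46 patients do not supply.

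**What to change.** 1. Add disease group (trial) to the Aim 2 model for every endpoint, alongside baseline GE T1/2 and gender. When gene x treatment is tested in all patients, add disease x treatment as well.
2. State in the text that Table 4 rests on single-population SDs, from healthy volunteers for GE T1/2. These should not be relabelled as within-disease values.
3. Recompute Table 4 with within-disease residual SDs from the trial's own data, at 23 v 23, or at 28 v 18 for *FAAH*.

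The cost is one degree of freedom for disease, a second for disease x treatment, and a few lines of SAP text. Disease group is already known for every participant. The change calls for no new pooled comparison of cannabidiol with placebo.
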